### **10.1.5 Dosimetric analysis**

Dosimetric analysis will be performed and compared to an external beam plan for each patient. The NTDmeans from dose volume histogram analysis for each individual patient for skin, heart, lung, and contralateral breast will be determined.

### **10.1.6 Mammography Interpretation**

The ability to interpret mammography after interstitial brachytherapy will be prospectively evaluated by the radiologist.

### **10.1.7 Disease-Free Survival and Mastectomy-Free Survival**

All disease recurrences and surgical interventions will be recorded. In disease-free survival (DFS), any tumor recurrence or death will be considered a failure. In mastectomy-free survival (MFS), the failures will be mastectomy and death. Ipsilateral breast recurrence rate (subdivided by in-field, peripheral and extra-field locations) ipsilateral nodal recurrence rate and distant metastasis rate will be calculated.

### **10.1.9 Overall Survival (OS)**

Death from any cause will be considered a failure.

### **10.2 Study Design**

The sample size will be approximately 300 patients. The toxicity rate will be summarized along with exact 95% confidence intervals. DFS, MFS and OS

results will be summarized using Kaplan-Meier curves with the usual Greenwood estimates of standard errors. Summary statistics will be given for cosmesis, quality of life, dosimetric, and mammography interpretation measures. All analyses will be conducted on an intent-to-treat basis; that is, all registered patients will be included in the analyses.

## Appendix I

### Data Safety and Monitoring Plan

#### Oversight And Monitoring Plan

The UWCCC Clinical Trials Monitoring Committee (CTMC) is responsible for monitoring data quality and patient safety for all UWCCC clinical studies. A summary of CTMC activities follows:

- Review of all clinical trials conducted at the UWCCC for progress and safety
- Review of all adverse events requiring expedited reporting as defined in the protocol
- Review of reports generated by the UWCCC data quality control review process
- Submit recommendations for corrective action to the Clinical Affairs Committee (CAC)
- Notify the Study Chair of the CTMC recommendation to the CAC
- Notify external sites participating in multiple-institutional clinical trials coordinated by the UWCCC of adverse events requiring expedited reporting and subsequent committee recommendations for study modifications.

#### Monitoring And Reporting Guidelines

##### **Phase I/II and Phase II Trials**

Data related to these trials are discussed at regularly scheduled Disease Oriented Working Group meetings where the result of each patient's treatment is discussed and the discussion is documented in the minutes. The discussion will include for each treatment arm/dose level, the number of patients, significant toxicities as described in the protocol, dose adjustments, and responses observed. Twice yearly, summaries will be submitted to the Clinical Trials Monitoring Committee for review.

### REVIEW AND OVERSIGHT REQUIREMENTS

#### Adverse Event – Reported By Phone Within 24 Hours

Adverse events requiring expedited reporting by phone within 24 hours (as described in the protocol) will also be reported by phone to the Clinical Trials Monitoring Committee administrator within one working day. Confirmation that all appropriate parties were notified will be done at this time. Hardcopies or electronic versions of NCI ADEERS form (#3500) and/or any other documentation available at that time will also be reviewed by the Committee Chair who will determine if immediate action is required. Within ten working days all subsequent SAE documentation that is available will be submitted with a completed UWCCC SAE Evaluation Checklist to the Committee Chair who will determine if further action is required. All information will be tracked in the UWCCC database.

If the AE occurs on a multiple-institutional clinical trial coordinated by the UWCCC, the Safety Coordinator will insure that all participating sites are notified of the event and resulting action within one working day of the determination.

#### Adverse Event – Reported within 10 Days

Adverse events requiring expedited AE reports in writing within 10 working days (as described in the protocol) will be sent to the UWCCC Safety Coordinator. Hardcopies or electronic versions of NCI ADEERS form (#3500) or other required forms will be submitted along with a copy of the SAE Evaluation Checklist. The Committee Chair will review these forms and determine if further action is required. This information will be tracked in the UWCCC database.

If the AE occurs on a multiple-institutional clinical trial coordinated by the UWCCC, the Safety Coordinator will insure that all participating sites are notified of the event and resulting action within one working day of the determination.

#### Study Progress – Quarterly Review

Study progress assessment to determine whether accrual projections are being met and to determine if the trial should be continued based upon the likelihood of timely completion are reviewed at quarterly Clinical Trials Monitoring Committee meetings. Cumulative reports of adverse events requiring expedited reporting and any new adverse event requiring expedited reporting are also reviewed at the committee's quarterly meetings.

An overall assessment of accrual, toxicities as described in the protocol, and responses will enable the committee members to assess whether significant benefits or risks are occurring that would warrant study closure. This information is provided by Disease Group meeting minutes, internal audit and/or response review reports. The committee may request external DSMB reports or further information from the Disease Groups, or Study Chair.

The Clinical Trials Monitoring Committee recommendations for modifications to the trial are forwarded to the Clinical Affairs Committee. The Study Chair is notified of this recommendation in order that he/she may alert all investigators, at the UWCCC and at external sites involved in the trial, about the potential action. At this time the Study Chair may submit to the Clinical Affairs Committee additional information that could affect the Committee's decision. The Clinical Affairs Committee will notify the Study Chair if they concur with the Clinical Trials Monitoring Committee recommendations, including suspension or closure. The Study Chair will notify all investigators involved with the study at UWCCC and external sites, the IRB, the sponsor and the funding agency and provide written documentation of these notifications to the Clinical Affairs Committee.

The UWCCC Clinical Research Committee (CRC), composed of Cancer Center senior leaders oversees these activities.

#### Review of Adverse Event Rates

Once a month, adverse event rates will be monitored utilizing the UWCCC Clinical Trials database. If any study has had two or more of the same AE reported in a month or more than six of the same AE in six months, the CTMC Chair will review the summary of SAEs, discuss events with Study Chair, and conduct a more detailed review with the Study Chair or the external DSMB if warranted. The Committee Chair will determine if further action is required.

If this occurs on a multiple-institutional clinical trial coordinated by the UWCCC, the Safety Coordinator will insure that all participating sites are notified of the resulting action.

### **EXPEDITED REPORTING OF ADVERSE EVENTS**

Depending on the nature, severity, and attribution of the event an ADR report will be phoned in, submitted in writing, or both according to Tables A-D below. Telephoned Adverse Events must also be reported by phone to the UWCCC Clinical Trials Monitoring Committee within one working day of the event. All adverse events must also be reported to the UW IRB, and any sponsor/funding agency not already included in the list.

**Written reports to:**

*[name].*

*[name] [contact] fax*

UWCCC Clinical Trials Monitoring Committee Administrator –

[contact] or deliver to [name]

UW IRB – Copy of final written report to Sponsor.

Summary of Reporting Requirements for Adverse Events on Trials Involving Commercial Agents with No IND Is Voluntary (Med Watch Form)			
EXPEDITED REPORTING FOR PHASE 2 AND PHASE 3 STUDIES			
Unexpected Event		Expected Event	
GRADES 2 - 3 Attribution of Possible, Probable, or Definite	GRADES 4 and 5 Regardless of Attribution	GRADES 1 - 3	GRADES 4 and 5, Regardless of Attribution
Expedited report within 15 working days to FDA.  (Grade 1 - Adverse Event Expedited Reporting NOT required.)	Report by phone to FDA within 24 hrs. Expedited report to follow within 15 working days.  This includes all deaths within 30 days of the last dose of treatment with an investigational agent regardless of attribution.  Any late death attributed to the agent (possible, probable, or definite) should be reported within 15 working days.	Adverse Event Expedited Reporting NOT required.	Report by phone to FDA within 24 hrs. Expedited report to follow within 15 working days.  This includes all deaths within 30 days of the last dose of treatment with an investigational agent regardless of attribution.  Any late death attributed to the agent (possible, probable, or definite) should be reported within 15 working days.  Grade 4 Myelosuppression or other Grade 4 events that do not require expedited reporting will be specified in the protocol.

**Note: Use Med Watch Form**

**For Hospitalization Only** – Any medical event equivalent to the CTC Grade 3,4,5 which precipitated hospitalization (or prolongation of existing hospitalization) must be reported regardless of requirements for phase of study, expected or unexpected and attribution.

Expedited reporting may not be appropriate for specific expected adverse events for certain later phase 2 and phase 3 protocols. In those situations the adverse events that will not have expedited reporting must be specified in the text of the approved protocol. An expected Grade 3 event that is using the generic reporting criteria, for instance. In a trial of

investigational agents where grade 3 diarrhea requiring hospitalization is expected, only diarrhea requiring ICU care (Grade 4) might be designated for expedited reporting.

## Appendix III: Initial Evaluation Form (Page 1)

Patient's Initials		Study ID #										

If this is a revised or corrected form, indicate by checking box. 
 
INSTRUCTIONS: Submit this form at time of patient's entry on study. Use -1 for unknown or not applicable unless otherwise specified in the code table. Record dates as mm/dd/yyyy.
												

 AGE AT REGISTRATION
 
MAMMOGRAPHIC FINDINGS
 
a. PRE-BIOPSY MAMMOGRAPHIC FINDINGS
 
1 No 2 Yes 9 Unknown
 
 Microcalcifications associated with malignancy  Microcalcifications not associated with malignancy  Mass  Parenchymal distortion  Multicentric lesion
 
b.  PRESENCE OF MICROCALCIFICATIONS ON POST-EXCISION / TYLECTOMY MAMMOGRAM?
 
1 No 2 Yes, associated with site of malignancy 3 Yes, not associated with malignancy 9 Unknown
 
 IF MULTIPLE LESIONS IN ONE QUADRANT, ARE LESIONS < 4CM APART?
 
1 No 2 Yes
 
TUMOR MEASUREMENTS (CLINICAL)
 
Maximum Diameter  . cm (On pre-biopsy mammogram)  . cm (On palpation, if not palpable enter '0')
 
a.  AFFECTED BREAST      b.  LOCATION OF LESION
 
 
1 Left	01 Upper outer quadrant	
 
2 Right	02 Upper inner quadrant	
 
3 Bilateral	03 Lower outer quadrant	
 
9 Unknown	04 Lower inner quadrant	
 
	05 Central	
 
			1 Left	01 Upper outer quadrant	2 Right	02 Upper inner quadrant	3 Bilateral	03 Lower outer quadrant	9 Unknown	04 Lower inner quadrant		05 Central
1 Left	01 Upper outer quadrant											
2 Right	02 Upper inner quadrant											
3 Bilateral	03 Lower outer quadrant											
9 Unknown	04 Lower inner quadrant											
	05 Central											
 
Mark Incision site and lesion location on diagrams above
 
 CHEMOTHERAPY
 
1 No 2 Yes, prior to XRT, end date _____ 3 Yes, after XRT 9 Unknown
 
 HORMONAL THERAPY
 
1 No 2 Yes, specify agent _____
 
 PRIOR RADIATION THERAPY TO EITHER BREAST?
 
1 No 2 Yes
 
 FAMILY HISTORY OF CANCER? (Mark relationship below)
 
If yes, breast CA? _____ other CA? _____
 
GYNECOLOGIC HISTORY: G_P Menopausal status: _____ Age at Menopause _____ Age at Menarche: _____ Age at 1st pregnancy _____ Exogenous Hormonal Exposure _____ Previous Breast Biopsies _____
 
PAST MEDICAL HISTORY: Conditions/ Surgeries: _____ Medications: _____ Allergies: _____
 
 HISTORY OF COLLAGEN VASCULAR DISEASE? (Systemic Lupus Erythematosis, scleroderma, dermatomyositis with elevated CPK level)
 
SMOKING HISTORY: ____ YRS ____ packs/day
												

## Appendix III: Initial Evaluation Form (Page 2)

PATHOLOGY DETAILS																		
SURGICAL PROCEDURES	Date																	
 FINE NEEDLE ASPIRATION	____-____-____																	
 CORE NEEDLE BIOPSY	____-____-____																	
 EXCISIONAL BIOPSY	____-____-____																	
 TYLECTOMY	____-____-____																	
 RE-EXCISION	____-____-____																	
PATH MEASUREMENT OF PRIMARY LESION																		
 .  cm	X	 .  cm	X	 .  cm														
Maximum diameter		Cross diameter		Cross diameter														
HISTOLOGIC CONFIRMATION		AXILLARY NODE DISSECTION																
		
 
 0	None (skip to Q#10)	
 
 1	Sampling / Level I nodes	
 
 2	Sampling / Level I, II nodes	
 
 3	Sampling / Level I, II, III nodes	
 
 4	Complete resection / Level I, II	
 
 5	Complete resection / Level I, II, III	
 
 6	Other, specify _____	
 
			0	None (skip to Q#10)	1	Sampling / Level I nodes	2	Sampling / Level I, II nodes	3	Sampling / Level I, II, III nodes	4	Complete resection / Level I, II	5	Complete resection / Level I, II, III	6	Other, specify _____
0	None (skip to Q#10)																	
1	Sampling / Level I nodes																	
2	Sampling / Level I, II nodes																	
3	Sampling / Level I, II, III nodes																	
4	Complete resection / Level I, II																	
5	Complete resection / Level I, II, III																	
6	Other, specify _____																	
 1 Invasive ductal		0																
 2 Medullary		1																
 3 Papillary		2																
 4 Colloid (mucinous)		Sampling / Level I nodes																
 5 Tubular		Sampling / Level I, II nodes																
TUMOR GRADE		SENTINEL NODE SAMPLING																
		
 
 1	No	
 
 2	Yes*	
 
			1	No	2	Yes*										
1	No																	
2	Yes*																	
PATHOLOGIC CHARACTERISTICS		*If yes, was Immunohistochemical (IHC) method used?																
 1 NOT PRESENT																		
 2 PRESENT		 NUMBER OF NODES EXAMINED																
 3 UNKNOWN		 NUMBER OF NODES POSITIVE																
 EXTENSIVE INTRADUCTAL COMPONENT		EXTRACAPSULAR EXTENSION																
 SKIN INVOLVEMENT		AJCC STAGE																
 LYMPHATIC VESSEL INVASION		T  N  M 																
 OTHER, SPECIFY: _____		WAS A PRE-TREATMENT PHOTOGRAPH TAKEN																
FINAL SURGICAL MARGINS		
 
 1	No	
 
 2	Yes	
 
			1	No	2	Yes										
1	No																	
2	Yes																	
EXCISION CAVITY DEFINED WITH SURGICAL CLIPS		
 
 1	No	
 
 2	Yes	
 
			1	No	2	Yes										
1	No																	
2	Yes																	
Signature of person completing this form:		____-____-____																
		Date form completed																

## Appendix III: Follow-up Form

 If this is a revised or corrected form, indicate by checking box.		INSTRUCTIONS: Submit this form at the appropriate follow-up interval and whenever there is a change in the patient's status. Use -1 for unknown or not applicable unless otherwise specified in code table. Enter dates in mm-dd-yyyy.
PATIENT INITIALS: _____ STUDY ID #: _____ DATE OF EVALUATION ____-____-_____		CURRENT TUMOR STATUS
 # MONTHS SINCE BRACHYTHERAPY PROCEDURE		 NO EVIDENCE OF DISEASE
 PATIENT QUALITY OF LIFE FORMED COMPLETED?		 IPSILATERAL BREAST TUMOR RECURRENCE
 PATIENT COSMESIS FORM COMPLETED?		 LOCAL (infield) - within the prescription isodose volume
1 EXCELLENT 2 GOOD 3 FAIR 4 POOR		 PERIPHERAL - between the prescription isodose volume and a volume 2 cm outside of the prescription isodose volume.
 PHYSICIAN COSMESIS FORM COMPLETED? (Initials: _____)		 NON-CONTIGUOUS/EXTRA-FIELD - beyond the peripheral volume described above.
 RTOG TOXICITY SCORE: SKIN		 OTHER SITES OF CANCER RECURRENCE
GRADE 0 None GRADE 1 Slight atrophy; Pigmentation change; Some hair loss GRADE 2 Patch atrophy; Moderate telangiectasia; Total hair loss GRADE 3 Marked atrophy; Gross telangiectasia GRADE 4 Ulceration		 NODAL (Specify location) _____
 RTOG TOXICITY SCORE: SUBCUTANEOUS TISSUE		 CONTRALATERAL BREAST _____
GRADE 0 None GRADE 1 Slight induration (fibrosis) and loss of subcutaneous fat GRADE 2 Moderate fibrosis but asymptomatic; <10% linear reduction; Slight field contracture		 DISTANT METS (Specify location) _____
GRADE 3 Severe induration and loss of subcutaneous tissue; >10% linear measurement; Field contracture		 NEW PRIMARY LESION (Specify location) _____
GRADE 4 Necrosis		 MAMMOGRAM SINCE LAST VISIT
		1 No 2 Yes * *If yes, date of study _____-_____-
		 SUSPICIOUS FINDINGS ON MAMMOGRAM
		0 Not applicable/no mammogram 1 Negative mammogram 2 Microcalcifications only 3 Mass density only 4 Both, mass and microcalcifications 5 Other, Specify _____
		 WERE PHOTOGRAPHS TAKEN DURING THIS VISIT?

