## **8.0 PATIENT ASSESSMENTS**

### **8.1 Study Parameters**

Assessment	Pre Rx	During/After Brachytherapy	Post RX 4-6 weeks	Post RX 6 mos.	Post RX 1 year
H & P (Initial Eval Form)	X				
Chest x-ray	X				
Lab studies a	X				
H & P (Follow-up Form)			X	X	Xc
Disease status	X		X	X	Xc
Toxicity Assessment		X	X	X	Xc
Mammograms	Xd			X	Xe
Cosmesis, Pt (Form)	X			X	Xb
Cosmesis, MD (Form)	X			X	Xb
Photographs	X	X	X	X	Xc
Questionnaire (QOL)	X	X	X	X	Xb

- a. CBC, platelets, PTT, PT, BUN, creatinine, lytes
- b. Yearly thereafter upto 5 years.
- c. Clinical examination and disease status assessment at 6 month intervals for the first 5 years and yearly intervals thereafter. (Can be done via clinic visit notes from other physicians involved in patient's care or via telephone follow-up).
- d. pre and post lumpectomy (if applicable)
- e. Every 6 months for 3 years and then yearly for 5 years (for treated breast) and yearly for opposite breast

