#### **At completion of brachytherapy**

- Patient QOL form (Appendix III)
- Treatment Toxicity Form
- Radiotherapy Treatment/Dosimetry Form (Appendix III)

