#### **At 4-6 wks, 6 mo., and 12 months after implant; q 6 months up to 5 years, then annually. Also at progression/relapse and at death**

- Follow-up Form (Appendix III) -- Can be done via clinic visit notes from other physicians involved in patient's care or via telephone follow-up

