## Appendix IV: Toxicity Scale

## RTOG Acute Toxicity Scoring

TISSUE	Grade 0	Grade 1	Grade 2	Grade 3	Grade 4
SKIN	No change over baseline	Follicular, faint or dull erythema/ epilation/dry desquamation/ decreased sweating	Tender or bright erythema, patchy moist desquamation/ moderate edema	Confluent, moist desquamation other than skin folds, pitting edema	Ulceration, hemorrhage, necrosis

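### The form assigned to the 4-6 week visit carries only the late toxicity scale, so an acute grade 3 skin reaction has no matching code there and may be missed or misgraded

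*Combined protocol and SAP*

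**What the plan says.** The assessment table in section 8.1 has a row "Toxicity Assessment", marked during or after brachytherapy, at 4-6 weeks, at 6 months, and from 1 year on. Section 8.3 says that toxicities from brachytherapy are graded by the criteria in Appendix IV. Section 10.1.2 repeats this and includes each follow-up visit.

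Appendix IV contains two scales. The acute scale covers skin only, and its grade 3 is "Confluent, moist desquamation other than skin folds, pitting edema". The late scale covers skin and subcutaneous tissue.

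Section 9.1 assigns forms to time points. At completion of brachytherapy it lists a "Treatment Toxicity Form". The Follow-up Form is due "At 4-6 wks, 6 mo., and 12 months after implant; q 6 months up to 5 years, then annually". Its two toxicity items are:
- skin: "GRADE 3 Marked atrophy; Gross telangiectasia"
- subcutaneous tissue: "GRADE 3 Severe induration and loss of subcutaneous tissue; >10% linear measurement; Field contracture"

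Section 2.2 sets a toxicity objective for grade 3 or higher at 3 years, against 5% for external beam. Section 10.2 promises a toxicity rate with exact 95% confidence intervals. It does not say whether acute events count or which records supply the rate.

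**The concern.** The plan asks for grading on a scale that includes acute reactions, then gives the visit a form without that scale. The course is 8 or 10 twice-daily fractions (section 5.5), and the completion form is filled in when it ends. A reaction that develops or worsens after that point, and resolves before 6 months, has one scheduled assessment at which it can be recorded: the 4-6 week visit.

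Section 9.1 also allows the Follow-up Form to be completed from other physicians' notes or by telephone. The categories printed on the form then matter more, because the person completing it may not have examined the patient.

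At stake is the completeness of the grade 3 or higher toxicity rate. If acute events belong in it, missing some of them can only lower it, and that favours brachytherapy in the comparison with 5%.

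**Working it through.** **Step 1. Compare the form with the two scales.** Skin grades as printed:

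| Grade | Appendix IV, acute | Appendix IV, late | Follow-up Form |
|---|---|---|---|
| 1-2 | erythema, desquamation, edema | atrophy, pigmentation, telangiectasia, hair loss | as late |
| 3 | confluent moist desquamation, pitting edema | marked atrophy, gross telangiectasia | as late |
| 4 | ulceration, hemorrhage, necrosis | ulceration | as late |

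The form's subcutaneous item also follows the late scale (induration, contracture, necrosis). Acute grade 4 therefore has near counterparts on the form: ulceration under skin and necrosis under subcutaneous tissue. Acute grades 1 to 3 have no matching descriptor. The gap that touches the toxicity objective is acute grade 3.

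**Step 2. Look for another scheduled form.** Section 9.1 lists the Treatment Toxicity Form only at completion of brachytherapy. Its content is not in the public text, so whether it carries the acute scale cannot be checked. If it does, it covers reactions up to that date and not the 4-6 week visit.

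**Step 3. Size, as an illustration.** The plan gives no margin, power or decision rule for the toxicity rate, so it has no figure to reproduce here. Inputs:
- n = 300 (section 10.2) and reference 5% (section 2.2).
- Recorded count x and number missed m: assumptions, because the documents give neither.

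True rate = (x + m)/300, so each missed patient lowers the recorded rate by 1/300 = 0.33 percentage points. The exact (Clopper-Pearson) 95% limits for k events in n are the 0.025 quantile of Beta(k, n − k + 1) and the 0.975 quantile of Beta(k + 1, n − k).

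| Recorded | Missed (assumed) | True count | True rate (exact 95% interval) |
|---|---|---|---|
| 15/300 = 5.0% (2.8-8.1%) | 3 (1%) | 18 | 6.0% (3.6-9.3%) |
| same | 6 (2%) | 21 | 7.0% (4.4-10.5%) |
| same | 9 (3%) | 24 | 8.0% (5.2-11.7%) |
| same | 15 (5%) | 30 | 10.0% (6.8-14.0%) |
| 9/300 = 3.0% (1.4-5.6%) | 3 (1%) | 12 | 4.0% (2.1-6.9%) |
| same | 6 (2%) | 15 | 5.0% (2.8-8.1%) |
| same | 9 (3%) | 18 | 6.0% (3.6-9.3%) |
| same | 15 (5%) | 24 | 8.0% (5.2-11.7%) |

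The smallest count whose whole interval lies above 5% is 24 (23 of 300 has a lower limit of 4.92%). The loss hides a clear excess over 5% only if the true count reaches 24 and the recorded count falls below it. With 1% or 2% missed from these starting points, the interval includes 5% both with and without the missed events, although the estimate moves by 1 or 2 points.

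**Step 4. The other reading of the endpoint.** If the rate at 3 years is meant to cover late toxicity only, acute reactions lie outside it and the change is zero in every row.

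**The case against.** The strongest reply is that the form is only one of several records.

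- Section 8.3 ties reporting to the monitoring board and the IRB to the Appendix IV grade, not to an entry on the Follow-up Form. A clinician who follows the protocol would grade confluent moist desquamation as 3 and report it.
- Photographs are due at 4-6 weeks and are reviewed for visible complications (section 8.5). Patients are seen daily during treatment.
- The form's field is labelled only as an RTOG skin score, so a clinician could enter the acute grade.
- The objective is set at 3 years, which may mean late toxicity.
- The institution's own experience in section 1.0 reports minimal acute toxicity.

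Much of this stands. A reader might infer that acute grade 3 events are scored 0 and drop out of the toxicity rate. The documents do not support that. No instruction says to enter 0, the form's code for unknown or not applicable is -1, and section 10.2 does not say that the rate is built from this form. Nor does safety reporting depend on the form.

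The reply does not remove the gap. Nothing says that safety reports or photographs feed the toxicity rate. Section 8.3 also refers to the appendix for the reporting rules, and the table in Appendix I exempts expected grade 1 to 3 events from expedited reporting. A field that prints late descriptors beside each grade invites a late-scale answer. Finally, section 2.2 does not limit the objective to late events, and Appendix IV includes an acute scale.

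**Conclusion.** The Follow-up Form cannot carry out the plan's own grading rule at the 4-6 week visit. Acute skin reactions seen then, in particular acute grade 3, have no matching code and may be missed or graded on the wrong scale.

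The effect on the toxicity rate is conditional. It is downward if acute events count and some are not captured elsewhere, and zero if only late events count. Its size is unknown. Under the assumption that 1%, 2% or 3% of patients are missed, a true 6.0%, 7.0% or 8.0% would be recorded as 5.0%. It would be wrong to conclude that an excess over 5% will disappear: that needs about 3% of patients missed from a true rate of about 8%, and the documents supply neither figure. This is an inexpensive correction worth making, not evidence of an established bias.

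**What to change.** Add the Appendix IV acute skin scale to the Follow-up Form for the 4-6 week visit. Alternatively, list the Treatment Toxicity Form at that visit in section 9.1, provided that it carries that scale.

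In sections 10.1.2 and 10.2, state that grade 3 or higher acute and late toxicity are reported as separate rates, each with an exact 95% interval, and name the records that supply them. Compare with the 5% external-beam reference whichever rate has the same scope as that reference. The documents do not say whether the 5% includes acute reactions, so that has to be stated too. Pooling the worst grade on either scale is not advisable: it would redefine the endpoint against a reference of unknown scope.

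The cost is one extra item at an existing visit and a few sentences in section 10.
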